For AML subjects only, after review of safety and clinical activity data, the SRC may select a recommended dose level for expansion cohorts of voruciclib monotherapy (6 subjects) and/or voruciclib + venetoclax combination therapy (up to an additional 12 subjects each for $\text{IS}_{2\text{w},2\text{w}}$ and $\text{IS}_{3\text{w},1\text{w}}$) in order to obtain additional safety, efficacy, PK, and pharmacodynamic/biomarker data. Formal stopping rules for excess toxicity in the AML combination therapy expansion cohort are provided in the protocol ([Section 4.5](#)).

Rationale for Dose Schedule Changes in Amendment 7

In the earlier dose-escalation phase of this study, in which voruciclib was administered QD for 28 days per 28-day cycle, there were no DLTs in the 50 mg QD dose cohorts in either B-cell or AML subjects. However, at 100 mg QD dose level, 2 subjects with AML had DLTs of pneumonitis ($n = 1$) and interstitial lung disease ($n = 1$), prompting a Sponsor decision to no longer pursue a QD dosing schedule in either disease group. Because there were no objective responses reported at the dose of 50 mg QD, intermittent dosing schedules ($\text{IS}_{2\text{w},2\text{w}}$ and $\text{IS}_{1\text{w},3\text{w}}$) were started with voruciclib 100 mg to determine whether doses of 100 mg or greater can be administered safely. These doses are projected to achieve plasma concentrations consistent with concentrations shown to demonstrate anti-proliferative effects in in vitro models.

(Note: Amendments 8, 9, and 10 were not implemented)

Rationale for the Addition of Voruciclib + Venetoclax Combination Therapy in Amendment 11

For the treatment of AML subjects, it is hypothesized that use of a CDK9 inhibitor (such as voruciclib) with its corollary effect on Mcl-1 inhibition when given in combination with a Bcl-2 inhibitor (such as venetoclax) could synergistically bring about disruption of the cell cycle and inhibition of pro-survival cell cycle pathways. Based on preliminary safety and tolerability data with voruciclib monotherapy, the $\text{IS}_{2\text{w},2\text{w}}$ dosing schedule will be used for the combination of voruciclib and venetoclax in AML patients.

Rationale for an Additional Voruciclib Schedule in Amendment 12

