4.2.1.1. Rationale for Dose and Schedule Changes in Amendment 7 – Voruciclib Monotherapy

Prior to Amendment 7, a total of 16 subjects had been administered voruciclib; 8 in Cohort 1 and 8 in Cohort 2, including 12 subjects with B-cell malignancies and 4 subjects with AML; with all 4 AML subjects enrolled in Cohort 2 following the implementation of Amendment 5. During the continuous daily dosing cohorts, there were no DLTs in the 50 mg QD dose cohort. At the 100 mg QD dose cohort, 2 subjects with AML had a DLT of pneumonitis, pre-empting further dose escalation on the continuous daily dosing schedule. In addition, one subject with DLBCL

enrolled at the 50 mg QD dose cohort experienced hypoxemic respiratory failure with pulmonary infiltrates in Cycle 4. There was no identified cause for this event, which was considered related to study drug and led to voruciclib discontinuation.

The mechanism of this pulmonary toxicity is not understood. PK data from the Phase 1 studies in solid tumors indicated that voruciclib has a very high volume of distribution (>100 L), suggesting higher exposure in tissues than in plasma. Interstitial pneumonitis has been reported post-marketing with the CDK4/6 inhibitors, which are approved in the US for the treatment of patients with breast cancer ([FDA Drug Safety Communications, September 2019](#)).

Because there were no objective responses reported at the dose of 50 mg QD, an IS was implemented to determine whether doses of 100 mg or greater could be administered safely. These doses were projected to achieve plasma concentrations needed for antitumor activity based on non-clinical models (data on file). The planned intermittent schedule allowed for complete clearance of the drug from the plasma and tissues during the 2-3 weeks off therapy and may mitigate the risk of toxicity. In the Phase 1 study P1446A-05/19/08 in various solid tumors, voruciclib was administered on a 2 weeks on/1 week off schedule with doses escalated up to 850 mg and the MTD was established at 600 mg. The intermittent schedule to be evaluated in Amendment 7 will further expand the treatment-free interval to 2 weeks (Cohorts 6-8) or 3 weeks (Cohorts 9-11) and evaluate voruciclib doses levels up to 200 mg.

Beginning with Amendment 7, subjects with AML and B-cell malignancies were to be evaluated in up to 6 new potential IS dose regimens separately.

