- Trough plasma concentration of 1 to 1.5 μM , concentrations shown to be synergistic in combination with venetoclax in preclinical models.

Once the safe and mBED of voruciclib in combination with venetoclax is identified by the SRC, which could be a dose less than 350 mg, dose escalation will stop and the SRC may recommend opening the dose expansion for the combination therapy (up to 12 subjects). At that time, subjects still actively dosing in the prior cohort may have their dose escalated to the next dose level after completing Cycle 1 (intra-subject dose escalation). Subjects may continue to receive

voruciclib plus venetoclax while there is evidence of clinical benefit (partial remission [PR] or better) by the end of Cycle 6 and acceptable toxicity as judged by the Investigator.

Amendment 12 – IS_{3w,1w} Dosing Schedule

In Amendment 12, the combination of voruciclib with venetoclax will be evaluated in subjects with relapsed and/or refractory AML using a voruciclib intermittent schedule of daily dosing on Days 1–21 in a 28-day cycle, with no voruciclib dosing on Days 22–28 of the cycle, designated as IS_{3w,1w} with the exception of Cycle 1 where voruciclib dosing begins on Day 3. In Cycle 1, venetoclax dose ramp-up will consist of venetoclax 100 mg on Day 1, then 200 mg on Days 2–21, then 400 mg on Days 22–28, with voruciclib beginning on Day 3.

The starting voruciclib dose level will be 150 mg in combination with venetoclax (i.e., 2 dose levels lower than the dose of 250 mg that has been shown to have no DLTs on IS_{2w,2w}). Dose escalation will follow the same 3+3 design as in the IS_{2w,2w} cohorts, and uses the same definition for DLT, MTD, and mBED.

In the IS_{2w,2w} dose escalation cohorts, no DLTs have been reported at doses ranging from 50 mg QOD to 250 mg QD, and enrollment was ongoing at the 300 mg dose level at the time of issuance of protocol Amendment 12.

The combination cohorts on IS_{3w,1w} will be numbered as listed below in [Table 4](#).

Table 4: Dose Cohorts with Combination Voruciclib + Venetoclax (Amendment 12)

Cohort Dose Level	Doses and Schedule
21	voruciclib 150 mg QD, administered IS _{3w,1w} + venetoclax administered QD × 28 days
22	voruciclib 200 mg QD, administered IS _{3w,1w} + venetoclax administered QD × 28 days
23	voruciclib 250 mg QD, administered IS _{3w,1w} + venetoclax administered QD × 28 days
24	voruciclib 300 mg QD, administered IS _{3w,1w} + venetoclax administered QD × 28 days

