4.4. Dose-Limiting Toxicity (DLT)

A DLT will be defined as any of the following treatment-emergent adverse events (TEAEs) occurring in Cycle 1 of voruciclib monotherapy or voruciclib + venetoclax combination therapy that are clearly unrelated to the underlying disease or extraneous causes:

- Symptomatic nonhematological Grade ≥ 3 laboratory abnormalities or asymptomatic nonhematological Grade ≥ 3 laboratory abnormalities that fail to improve to Grade ≤ 2 within 72 hours
- Grade 3 vomiting lasting >48 hours despite recommended antiemetic support or any occurrence of Grade ≥ 4 vomiting
- Grade 3 diarrhea lasting >48 hours despite recommended antidiarrheal support or any occurrence of Grade ≥ 4 diarrhea
- All other Grade ≥ 3 nonhematological adverse event (AE) not listed above
- Grade 3 or higher TLS regardless of prophylaxis
- Hy's law cases
- Febrile neutropenia of any duration (not applicable to AML subjects)
- Grade 4 neutropenia lasting ≥ 7 days; or lasting ≥ 42 days and not due to progressive disease in AML subjects
- Grade ≥ 3 thrombocytopenia with Grade ≥ 2 bleeding or Grade 4 thrombocytopenia of any duration (not applicable to AML subjects)
- Grade 4 thrombocytopenia lasting ≥ 42 days (AML subjects only)
- Grade 4 anemia unexplained by underlying disease

Hy's law cases of drug-related hepatocellular injury are defined as elevated ALT or AST $\geq 3 \times$ ULN, elevated total bilirubin $>2 \times$ ULN without findings of cholestasis, and no other reason can be found to explain the combination of increased aminotransferase and serum total bilirubin, such as viral hepatitis, alcohol abuse, ischemia, pre-existing liver disease, or another drug capable of causing the observed injury.

Additionally, discontinuation of study drug in Cycle 1 due to an AE that is clearly unrelated to the underlying disease, or an extraneous cause will be considered a DLT.

Safety will be assessed by AEs graded according to National Cancer Institute Common Terminology Criteria for Adverse Events (NCI CTCAE) v5.0; laboratory safety tests including hematology (complete blood count [CBC]), serum chemistry; physical examination; vital signs; ECOG performance status; and 12-lead electrocardiogram (ECG).

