4.11. Interstitial Lung Disease/Pneumonitis

Interstitial lung disease (ILD)/pneumonitis has been reported post-marketing with the CDK4/6 inhibitors, which are approved in the US for the treatment of patients with breast cancer (FDA Drug Safety Communications, September 2019). With the continuous dosing schedule of voruciclib, 2 subjects with AML had DLTs of pneumonitis (n = 1) or ILD (n = 1) at the 100 mg QD dose level. Of note, the 2 subjects had confounding factors that may have contributed to this toxicity, including a history of secondary AML following a myelodysplastic syndrome, heavily pretreated disease, allogeneic stem cell transplantation in the preceding 12 months, and evidence of differentiation syndrome occurring 1 to 2 weeks after voruciclib initiation. These DLTs prompted the Sponsor decision to no longer pursue a QD dosing schedule in either disease group. In addition, one subject with DLBCL enrolled at the 50 mg QD dose cohort experienced hypoxemic respiratory failure with pulmonary infiltrates in Cycle 4. There was no identified cause for this event, which was considered related to study drug and led to voruciclib discontinuation.

The mechanism of this pulmonary toxicity is not understood. PK data from the Phase 1 studies in solid tumors indicated that voruciclib has a very high volume of distribution (>100 L), suggesting higher exposure in tissues than in plasma.

Subjects should be monitored for symptoms indicative of ILD/pneumonitis (e.g., hypoxia, cough, dyspnea), with management as indicated in Table 12. In subjects with new or worsening respiratory symptoms and in whom pneumonitis is suspected, voruciclib administration is to be suspended and permanently discontinued if pneumonitis is confirmed.

Table 12: Monitoring and Management of Interstitial Lung Disease/Pneumonitis

Grade 1	Monitor patients weekly with history and physical examination, pulse oximetry and imaging
Grade 2	Hold voruciclib until at least \leq Grade 1 Consider prednisone 1-2 mg/kg/day with taper by 5-10 mg/week over 4-6 weeks Consider bronchoscopy with bronchoalveolar lavage (BAL) Consider empiric antibiotics Monitor Q3 days with history and physical examination, pulse oximetry and imaging

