4.12. Subject Replacement

Subjects who discontinue study therapy prior to completing Cycle 1 (Day 28) for reasons other than the development of a DLT will be replaced. Subjects who miss one or more doses for reasons other than DLT, must receive at least 75% of the total planned voruciclib dose in Cycle 1 to be assessed for DLT. Subjects with no DLT who fail to receive at least 75% of the planned Cycle 1 voruciclib dose will be replaced.

For Cohort 12, subjects must receive 100% of Cycle 1 doses (i.e., all 6 doses) to be DLT evaluable; subjects with no DLT who fail to receive 100% of Cycle 1 voruciclib doses will be replaced.

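### Read literally, the DLT attribution clause can leave Cycle 1 events of uncertain cause out of the DLT count, which conflicts with how the protocol treated its own confounded lung events

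*Protocol*

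**What the plan says.** Protocol 4.4 lists the qualifying Cycle 1 events and restricts them to those "that are clearly unrelated to the underlying disease or extraneous causes". The synopsis uses the same words. A further sentence makes a DLT of "discontinuation of study drug in Cycle 1 due to an AE that is clearly unrelated to the underlying disease, or an extraneous cause". Neither place gives a default for an event whose cause is in doubt. The Related/Not Related scale in Protocol 6.6 is not tied to the DLT definition.

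Protocol 4.12 adds: "Subjects who discontinue study therapy prior to completing Cycle 1 (Day 28) for reasons other than the development of a DLT will be replaced". SAP 6.2 repeats this and computes the DLT rate on the DLT Evaluable Set.

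On the two AML lung events at 100 mg QD, the synopsis states that "2 subjects with AML had DLTs of pneumonitis" and ILD occurred. Section 4.2.1.1 reports that "2 subjects with AML had a DLT of pneumonitis, pre-empting further dose escalation on the continuous daily dosing schedule". Section 4.11 records that "the 2 subjects had confounding factors that may have contributed to this toxicity": secondary AML, heavy pretreatment, allogeneic transplant in the preceding 12 months and evidence of differentiation syndrome. It then says: "These DLTs prompted the Sponsor decision to no longer pursue a QD dosing schedule in either disease group".

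**The concern.** The clause asks for proof that an event is not due to disease or another cause before it counts. In relapsed or refractory AML, a Grade 3 lung infiltrate, hypoxia or sepsis often has a plausible competing explanation. Such an event can be marked Related under 6.6 and still fail the test in 4.4.

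The DLT count feeds four decisions: the escalation rule (4.3.2), the MTD (4.6), the limit of 1 DLT in 6 subjects in the mBED criteria (4.3.2), and the Table 7 boundary (4.5), which uses criteria consistent with the DLT definition. A downward bias moves all four toward a finding of safe. The 150 mg starting level on the 3-weeks-on schedule also rests on a DLT count, being described as "2 dose levels lower than the dose of 250 mg that has been shown to have no DLTs" on the 2-weeks-on schedule.

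Text and practice disagree, so a later SRC could follow either one and reach a different count from the same data. One of the confounders named in 4.11, prior allogeneic transplant, is permitted in the combination cohorts (note to exclusion criterion 11).

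**Working it through.** **Text against practice.** Under 4.4 an event must be clearly unrelated to disease and to extraneous causes. Section 4.11 names factors that may have contributed to both lung events, and the synopsis calls differentiation syndrome a contributing factor. A strict reader would struggle to call either event clearly unrelated, yet both were counted. Section 4.2.1.1 puts 4 AML subjects in Cohort 2, so the AML record there is 2 DLTs in 4, not 0 in 4.

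**Size, as an illustration.** The plan gives no figure on this point to reproduce. Inputs:

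- Escalation rule (4.3.2): 0 DLTs in 3 subjects, or no more than 1 in 6.
- p, the true rate of drug-caused DLT-type events: assumed.
- a, the share of those events with an uncertain cause: assumed, because the documents give none.

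The probability that the DLT rule permits escalation at a counted rate r is

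P(r) = (1−r)³ + 3r(1−r)² × (1−r)³.

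If the subject stays in the set as having no DLT, r = p(1−a). If every such subject is replaced, r = p(1−a)/(1−pa).

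For p = 0.33 and a = 0.5:

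- All counted: r = 0.33; 0.301 + 0.444 × 0.301 = 0.43.
- Kept: r = 0.165; 0.582 + 0.345 × 0.582 = 0.78.
- Replaced: r = 0.165/0.835 = 0.198; 0.517 + 0.382 × 0.517 = 0.71.

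| True rate p | Ambiguous share a | All counted | Kept as no DLT | All replaced |
|---|---|---|---|---|
| 0.33 | 0.25 | 0.43 | 0.61 | 0.56 |
| 0.33 | 0.50 | 0.43 | 0.78 | 0.71 |
| 0.40 | 0.50 | 0.31 | 0.71 | 0.60 |

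At p = 0.40 with subjects kept, the result runs from 0.49 (a = 0.25) to 0.91 (a = 0.75).

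**Table 7.** Take the boundary as crossed when the count reaches the tabled value, checked at each of subjects 4 to 12. At a true rate of 40% the chance of crossing is 0.655 if all events count and 0.144 if half count.

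**The other direction.** Suppose the drug-caused rate is 15% and another 15% of subjects have an ambiguous event that is really due to disease. If only the drug events count, P(0.15) = 0.614 + 0.325 × 0.614 = 0.81. If both count, P(0.30) = 0.343 + 0.441 × 0.343 = 0.49. Counting uncertain events therefore has its own error.

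**The case against.** The strongest reply is that practice was conservative. A reader might infer from the wording that the two lung events were left out, or that every event of uncertain cause is left out. The documents do not support either inference. The synopsis, 4.2.1.1 and 4.11 all count both events, and the sponsor acted on them. Differentiation syndrome is also not cleanly a competing cause, since 4.10 discusses it as something voruciclib may induce. The cases therefore show only that text and practice do not match.

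A reader might also infer that the report of no DLTs from 50 mg QOD to 250 mg QD was produced by this clause. That cannot be verified. Section 4.3.2 says the new cohorts use the same DLT definition as the earlier combination cohorts, but only the current protocol text is available. Nothing shows that any event was excluded on attribution. The statement covers Cohorts 12–17; the 300 mg cohort was still enrolling.

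The DLT count is also not the only gate. Escalation needs SRC approval, the SRC sees all available safety, PK and PD data (4.3.2) and can advise a hold (4.3.1.1; SAP 7.10), and all TEAEs are tabulated by cohort (10.4.1). This mitigates the bias but does not remove it: the DLT rate, the MTD and the 1-in-6 limit are still defined on the count. The replaced column is an extreme, because 4.12 replaces only subjects who stop early or fall short of the required Cycle 1 dose.

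**Conclusion.** The concern holds as a conflict between the written DLT definition and its recorded use. Followed literally, the definition can leave out drug toxicities whose cause is uncertain, and 4.12 can remove those subjects from the denominator. For drug-caused events the direction of the bias does not depend on the assumed share; its size does. With half the events ambiguous, the chance that the DLT rule permits escalation rises by 0.28 to 0.35 at a true rate of 33% and by 0.29 to 0.40 at 40%. These are properties of the counting rule before SRC judgment, not estimates of what happened in this trial. The opposite error, counting disease events, is also real and is the reason to document each exclusion.

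**What to change.** - **Protocol 4.4 and synopsis:** reconcile the attribution clause and the discontinuation sentence with the practice in 4.11. The text should no longer remove events of uncertain cause from the DLT count by default. Any exclusion as disease-related or extraneous should be documented and accepted by the SRC.
- **Protocol 4.12, with SAP 3.1.4 and 6.2:** bring the replacement sentence into line, so that a subject who stops in Cycle 1 for an event of uncertain cause does not drop out of the count unnoticed.
- **SAP 8.7.1:** tabulate by cohort the Cycle 1 events that meet a listed criterion but were excluded on attribution, including those in replaced subjects.
- **Recorded data:** have the SRC check the recorded Cycle 1 events in Cohorts 12–17 before relying on the no-DLT statement.

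The cost is protocol and SAP wording, one table and one SRC review of data already collected. The downside is that the reported DLT rate may be less favourable and some cohorts may expand to 6. Some disease events may also be counted, which could stop escalation earlier or lower the MTD.

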4.5. Expansion Cohort and Early Stopping Boundaries for Toxicity

Once the safe and mBED of voruciclib in combination with venetoclax on IS_{2w,2w} and IS_{3w,1w} has been declared in subjects with AML, an expansion cohort of up to 12 additional subjects for each of the 2 voruciclib dose schedules will be enrolled to further characterize the safety, efficacy, PK, and pharmacodynamics of the mBED on IS_{2w,2w} and IS_{3w,1w}.

Sequential boundaries will be used to monitor the rate of unacceptable toxicities in AML subjects enrolled on expansion cohorts, using criteria consistent with those used to define DLTs in escalation cohort subjects, with focus on potential cumulative toxicities over time. If an excessive number of unacceptable toxicities are observed, the SRC will have the option of either halting study accrual or reducing the dose to reduce the level of toxicity. The boundaries at which enrollment into an expansion cohort will be halted or safe and mBED reduced are listed in Table 7. This is a Pocock-type boundary that yields 0.2 or greater probability of crossing the boundary when the rate of DLT/unacceptable toxicity is equal to the acceptable rate of 20% (Ivanova 2005).

Since these boundaries are very conservative, to avoid a high false positive rate in the early stage of the enrollment period due to a small sample size, the Pocock boundary described below will be implemented after 4 subjects have been enrolled; for subjects 1-3 the decision to halt study accrual or reduce the dose will be based on clinical judgment, SRC, and Sponsor.

Table 7: Early Stopping Boundaries for Toxicity – Expansion Cohort

# Subjects	1	2	3	4	5	6	7	8	9	10	11	12
Boundary	-	*	*	3	3	3	4	4	4	5	5	5

*Subjects 1 – 3 will be based on clinical judgement.

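### Protocol 4.5 says the Table 7 toxicity boundary is crossed with probability 0.2 or greater at a 20% toxicity rate; the tabled rule, applied from subject 4, is crossed with probability 0.144

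*Protocol*

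**What the plan says.** Protocol Section 4.5 provides for "an expansion cohort of up to 12 additional subjects for each of the 2 voruciclib dose schedules". Unacceptable toxicities in these cohorts are monitored with criteria consistent with the DLT definition. "The boundaries at which enrollment into an expansion cohort will be halted or safe and mBED reduced are listed in Table 7", and the row of limits reads "Boundary - * * 3 3 3 4 4 4 5 5 5" for 1 to 12 subjects. The section describes a Pocock-type boundary and states that it "yields 0.2 or greater probability of crossing the boundary when the rate of DLT/unacceptable toxicity is equal to the acceptable rate of 20" per cent.

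The next paragraph calls the boundaries very conservative. To avoid a high false-positive rate early in enrollment, it says that "the Pocock boundary described below will be implemented after 4 subjects have been enrolled", and that "for subjects 1-3 the decision to halt study accrual or reduce the dose will be based on clinical judgment, SRC, and Sponsor".

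The synopsis (Expansion Cohorts) and Protocol 4.3.1.2 send the reader to this section for the formal stopping rules. SAP 3.1.3 describes the expansion cohorts and SAP 7.10 describes review by the Study Review Committee (SRC). Neither gives a boundary or a crossing probability that would replace the sentence in Protocol 4.5.

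**The concern.** Two things looked wrong in the sentence on crossing probability.

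First, its direction. When the true toxicity rate is the acceptable 20%, crossing the boundary is a false alarm. One would expect a sequential rule to be described by a ceiling on that probability, yet the sentence gives a floor. A floor also sits badly with the next paragraph, which wants to keep false positives low.

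Second, its value. Everything needed to compute the probability is printed in Section 4.5, and the result is not 0.2 or more.

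This sentence is the only operating characteristic given for the only formal numerical rule in the expansion cohorts. An SRC member or ethics reviewer reading it would take the chance of a false stop at an acceptable rate to be at least one in five, when for the tabled counts it is about one in seven. They are also given no crossing probability at any higher toxicity rate, which is what they would need to judge the rule.

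**Working it through.** **Inputs, all from Protocol 4.5.** Acceptable rate p = 0.20. Maximum 12 subjects per cohort. Limits b(n): 3 at n = 4, 5, 6; 4 at n = 7, 8, 9; 5 at n = 10, 11, 12. No numerical limit at n = 1 to 3. A crossing is taken to occur when the cumulative number of events reaches b(n). Assumptions added here: subjects are independent with a common rate, and the count is checked after every subject.

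**Method.** Let S(n,k) be the probability of k events after n subjects with no crossing so far. Then S(n,k) = 0.8 S(n−1,k) + 0.2 S(n−1,k−1) for k below b(n). The first look is a binomial tail. After that a crossing at n can come only from one event short of the limit, so its probability is 0.2 × S(n−1, b(n)−1).

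| n | Limit | Calculation | First crossing at n |
|---|---|---|---|
| 4 | 3 | 4(0.2³)(0.8) + 0.2⁴ | 0.0272 |
| 5 | 3 | S(4,2) = 6(0.04)(0.64) = 0.1536; × 0.2 | 0.0307 |
| 6 | 3 | S(5,2) = 10(0.04)(0.512) = 0.2048; × 0.2 | 0.0410 |
| 7 | 4 | at most 2 events at n = 6 | 0 |
| 8 | 4 | S(7,3) = 0.2 × 15(0.04)(0.4096) = 0.04915; × 0.2 | 0.0098 |
| 9 | 4 | S(8,3) = 0.8(0.04915) + 0.2(0.27525) = 0.09437; × 0.2 | 0.0189 |
| 10 | 5 | at most 3 events at n = 9 | 0 |
| 11 | 5 | S(9,3) = 0.8(0.09437) + 0.2(0.29360) = 0.13422; S(10,4) = 0.2 × 0.13422 = 0.02684; × 0.2 | 0.0054 |
| 12 | 5 | S(10,3) = 0.8(0.13422) + 0.2(0.30199) = 0.16777; S(11,4) = 0.8(0.02684) + 0.2(0.16777) = 0.05503; × 0.2 | 0.0110 |

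The unrounded terms sum to **0.14396**. A simulation of 400,000 cohorts gave 0.145.

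**Attempts to reproduce 0.2 or greater at p = 0.20.**

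| Reading | Crossing probability |
|---|---|
| Table 7 from subject 4 | 0.144 |
| First look at subject 5 (3 events at n = 4 still meet the limit at n = 5) | 0.144 |
| Add 2 events at n = 2 and 3 events at n = 3 | 0.158 |
| Add 2 events at n = 2 and at n = 3 | 0.186 |
| Crossing only when the limit is exceeded | 0.035 |
| One look, at n = 12 | 0.073 |

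None of these reaches 0.2. Checking after every subject is the most frequent schedule possible, so grouped or delayed looks can only lower 0.144. The rule as implemented reaches 0.2 at a true rate of about 22.7%.

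**Is a ceiling the likelier meaning?** Take boundaries that use the same pointwise tail probability at every look. The Table 7 counts, with 2 events assumed at n = 2 and n = 3, give 0.186. The next looser boundary in that family has 4 rather than 5 at n = 10 and gives 0.2006. The tabled counts are thus the loosest member of the family that stays under 0.2, which fits a ceiling and not a floor.

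**Tabled rule from subject 4, other rates.**

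| True rate | 10% | 20% | 25% | 30% | 40% | 50% |
|---|---|---|---|---|---|---|
| Crossing probability | 0.020 | 0.144 | 0.254 | 0.385 | 0.655 | 0.856 |

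**The case against.** The strongest reply is that this is one misworded phrase. If the sponsor meant at most 0.2, the rule meets it with room to spare, and a false-stop probability of 0.144 serves the stated wish to limit false positives. That stands, and it limits the point to the stated operating characteristic.

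A second reply is that 0.144 is not the whole chance of stopping. Subjects 1 to 3 are covered by clinical judgement, and the SRC may advise holding enrollment at any time (Protocol 4.3.1.1, SAP 7.10). This is true, but the sentence describes the boundary, and those stops are not part of it. With two expansion cohorts, the chance that at least one crosses at 20% is 1 − (1 − 0.144)² = 0.267. That does not rescue the sentence either, because Table 7 applies to a single cohort.

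A reader might also infer more than the documents support:

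- **That the rule is less sensitive than claimed.** Crossing at the acceptable rate is a false stop, not detection. The protocol states no detection probability at any higher rate, so nothing is contradicted there.
- **That early looks were removed and the table was not recomputed.** Table 7 shows only asterisks at subjects 2 and 3. The documents do not say what preceded them.
- **That subjects still in follow-up are counted as toxicity-free.** The word enrolled appears in the sentence on when monitoring starts, while the table row refers only to the number of subjects. The denominator is undefined, which is an ambiguity and not a demonstrated dilution of the rule.

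**Conclusion.** The stated operating characteristic is wrong. At a 20% toxicity rate the Table 7 boundary, applied from subject 4, is crossed with probability 0.144, not 0.2 or more. No single-cohort reading that was tried gets above 0.186. The result rests on independent subjects, a common toxicity rate and a check after every subject; less frequent checks would widen the gap. It excludes discretionary stops in subjects 1 to 3, whose contribution cannot be quantified from the documents.

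That the phrase was meant as a ceiling of 0.2 is likely but inferred from the counts and from the stated wish to limit false positives. The method paper cited in Section 4.5 was not available. The error does not by itself show that the Table 7 counts are unsuitable.

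**What to change.** Replace the sentence on crossing probability in Protocol 4.5 with the figures for the tabled rule as implemented from subject 4: 0.144 at a 20% toxicity rate, 0.385 at 30%, 0.655 at 40% and 0.856 at 50%. Add that stops by clinical judgement in subjects 1 to 3 are not included. If a ceiling of 0.2 was the design target, say so in those terms.

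As a clarification, add a clause to Table 7 stating whether the number of subjects means subjects enrolled or subjects evaluable for toxicity.

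The cost is one sentence and one clause. The counts, the sample size and the conduct of the expansion cohorts need not change on account of this point.
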